MACE, the composite endpoint that includes Death (all cause), Myocardial Infarction (MI) and Revascularization for myocardial ischemia, will be the primary outcome measure after randomization and the index CABG. Each randomized subject (either in Endoscopic or in Open harvesting group) will be followed after the index CABG to capture the time-to-MACE event where an ‘EVENT’ will be defined as either death (all cause) or an MI or a revascularization procedure during the follow-up period. Total follow-up period will be 6.5 years of which the first 4.5 years will be active follow-up (using in-clinic visit or by telephone) period and will be carried out by the site personnel. The remaining 2 years will be passive follow-up which will be carried out centrally by the chair’s office staff using the VA patient database. A minimum of 1 year of active follow-up will be used for subjects who will be randomized at the tail end of the 3-year projected enrollment period of the study. The subjects

who will either be lost to follow-up or will not experience an 'EVENT' before the end of the follow-up period will be considered as right censored.

The primary analysis of such time-to-Mace event data will include the events only from the active follow-up period (which is 4.5 years). The secondary analysis will include events from the entire 6.5 years of follow-up period.

Survival analysis techniques will be used to analyze the time-to-MACE event data for both primary and secondary analyses.

Kaplan-Meier analysis, a nonparametric method, will be used to estimate the survival (not experiencing MACE) over time in the two harvesting groups and a log-rank statistic will be used to test the equality of the survival function estimates in the two groups (the null hypothesis).

Cox's Proportional Hazards models will be used to investigate the effect of harvesting technique on the time until MACE adjusted for other potential influential variables, such as, age, gender, harvester's experience etc.

3. Secondary Outcomes Measures

One and Three-year MACE: This composite endpoint consists of

- i. Death (all cause);
- ii. Myocardial Infarction and
- iii. Revascularization for myocardial ischemia.

Subjects who suffer any one of these three outcomes within the first year or in the first three years after the index CABG will be counted towards calculating the proportions of subjects with MACE (yes/no) in each harvesting technique group – subjects with endoscopic vein grafting or subjects with open vein grafting. Only the first event will be considered as the MACE event. These two proportions will be compared using a chi-square test.

Post-operative Leg Wound Complications: All subjects in both harvesting technique groups – EVH or OVH – will be examined for complications of the leg wound from harvesting at discharge and at six weeks post-surgery. Post-operative leg wound complication status (yes/no) will be recorded at discharge and at six weeks post-surgery. Proportion of subjects with leg wound complications will be computed for each treatment group and these proportions at each time point will be compared using chi-square tests. The impact of confounding variables, such as, BMI, diabetes status, smoking status, on the post-operative leg wound infection will be analyzed using a logistic regression.

Severity of Incisional Leg Pain: Severe leg pain, due to incisions made during vein grafting, data will be collected at discharge and at six-week post CABG. Proportion of subjects with severe pain (pain score 3 and above = yes) at each time point will be compared using chi-square statistics.

Quality of Life: QoL scores using VR-12 and Seattle Angina Questionnaire will be computed at baseline, six week, and 12 months post-surgery for the subjects in the two harvesting technique groups (EVH and OVH). Subjects in both groups will be categorized as "improved", "no change" and "worse" based on their baseline scores. The proportion of subjects in these three categories will be compared between the two groups using chi-square statistics. The actual scores from these measures will also be used to compare subjects in the two harvesting technique groups using analyses of covariance techniques, where the baseline (pre-surgery) scores will be used as a covariate.

E. Interim Monitoring

An independent oversight committee, a Data Monitoring Committee (DMC), will be monitoring study progress at predetermined time points over the entire duration of the study. The committee will receive analyses of the primary outcome measures and the important secondary outcome measures on a routine basis. In general, this committee meets at six to nine months after the start of subject recruitment and yearly thereafter. So, in total, this committee will meet maximum four times during the four years of the study duration. The committee will receive reports about three weeks prior to their annual meetings and at six monthly intervals in between the annual meetings. Since the primary outcome measure (MACE) are times-to-MACE event, sufficient data for DMC's first review will not be available until the study has been ongoing for at least 2 years. So there will be approximately 8 interim analyses of the primary outcome measure based on which the DMC will decide on study's continuation.

F. Criteria for Study Termination

When repeated significance tests are performed on accumulating data as part of a routine monitoring function, the overall type-I error rate is inflated and the probability of a false positive finding is also increased. A number of methods have been developed to provide guidance on study termination rules based on multiple looks on the primary outcome measures for the review committees while keeping the overall type-I error rate maintained at 5%. For example, Haybittle-Peto or Lan-DeMets group sequential boundaries will provide study stopping guidance/criteria for the DMCs to implement. An example of typical Lan-DeMets boundary for six looks is illustrated in Figure 2. The DMC will make the final decision on the type of stopping rule that will be used for the REGROUP trial.

[figure not shown]

Figure 2: Lan-DeMets group sequential boundary for eight interim looks

This group sequential boundary is used as a guide for study termination at any interim look. If the z-statistic at any interim look falls outside either the lower or the upper boundary, then the study should be considered for termination.

G. Handling of Missing Data

Every effort will be made to minimize the occurrence of missing data, particularly for the primary and main secondary outcome measures. For the primary outcome (MACE), every effort will be made to contact the subjects over the phone every three months until subject termination. In the event of a potential drop out, every effort will be made to capture the MACE data from the VA databases.

H. Reporting of Any Deviations from the Original Statistical Plan

A more detailed statistical analysis plan (SAP) will be generated which will include the details of each statistical analysis plan for each outcome measure along with the suggested table shells for any reports that will be produced during the study and at the end of the study. Any deviations in the statistical plan from the protocol will be specified in the SAP. Any deviations from the SAP will be specified in the main manuscript which will be prepared and published at the end of the study.

XVIII. PUBLICATIONS

A. Publication Policy

It is the policy of the Cooperative Studies Program not to reveal outcome data to site investigators until the data collection phase of the study is complete. This policy is meant to prevent possible biases that might affect data collection. Members of the DMC will be reviewing outcome results to ensure that the study will be terminated early if a treatment is identified as prohibitively dangerous or if a definitive answer is reached prior to the scheduled study termination date.

All presentations and publications resulting from this study will follow CSP policy as specified by the CSP guidelines. The presentation or publication of any or all data collected by site investigators on subjects entered into a Department of Veterans Affairs Cooperative Study is under the direct control of the study's Executive Committee. No individual site investigator has the right to use the study's data to perform analyses or interpretations, or to make public presentations or seek publication of any or all of the data without specific approval of the Executive Committee.

The Executive Committee has the authority to establish any number of publication committees, which usually will comprise of subgroups of site investigators and some members of the Executive Committee, for the purpose of producing manuscripts for presentation and publication. Any presentation or publication related to this study should be circulated to the Executive Committee for review, comments and suggestions at least four weeks prior to submission of the manuscript to the presenting or publishing body.

All publications must give proper recognition to the funding source and should list all study participating site personnel (not necessarily as authors of the manuscript). If an investigator's major salary support and/or commitment is from the VA, it is obligatory that the investigator lists the VA as his/her primary institutional affiliation. Submission of manuscripts or abstracts must follow the usual VA policy; ideally, a subtitle states, "A Department of Veterans Affairs Cooperative Study." The CSP also requires that every manuscript be reviewed and approved by the CSPCC Director prior to submission as a final quality control step. Mechanisms for appeal by an investigator will follow procedures defined by the VA Office of Research and Development.

Participation in a Department of Veterans Affairs Cooperative Studies Program clinical trial is voluntary. Any investigator who cannot accept these operational guidelines regarding publication policy should not volunteer to participate in the study.

B. Planned Publications

Primary publication: Upon completion of the study, a manuscript will be prepared that focuses on the primary outcome, i.e. endoscopic saphenous vein harvesting vs. open saphenous vein harvesting MACE rates during the follow-up period.

Other publications: Other planned publications will include at least the following: Quality of Life with EVH and OVH, leg wound complications, 1 and 3 year MACE.

XIX. REFERENCES

[Alexander 2005] Alexander JH, Hafley G, Harrington RA, PREVENT-IV Investigators. Efficacy and safety of edifoligide, an E2F transcription factor decoy, for prevention of vein graft failure following coronary artery bypass graft surgery: PREVENT-IV: a randomized controlled trial. *JAMA* 2005;294:2446-54.

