The other secondary outcome measures are MACE at one and three-year post surgery, leg wound healing complications and Quality of Life.

Two leading vendors (Maquet and Terumo) are currently marketing EVH device technologies for CABG. Device-related and procedural information will be collected during the study.

Subjects will receive concomitant optimal medical therapies (OMT) in both groups as recommended by the current 2011 American College of Cardiology/American Heart Association guidelines [Smith 2011]. OMT will include formal smoking cessation counseling and the administration of aspirin, beta blockers, angiotensin converting enzyme inhibitors, and lipid-lowering medications.

FIGURE 1. STUDY FLOW DIAGRAM

VI. Subject Population

All subjects who are candidates for CABG and who will undergo surgery at a VAMC with demonstrated expertise for both OVH and EVH and qualify to participate in CSP-sponsored research will be invited to participate in the REGROUP study.

A. Inclusion Criteria:

- Age 18 years or older
- Elective or Urgent CABG-only
- Median sternotomy approach
- At least one coronary bypass planned using saphenous vein graft for conduit
- Experienced EVH/OVH harvester and participating surgeon available for procedure

B. Exclusion Criteria:

- Combined valve procedure planned
- Moderate or severe valve disease (see definition of moderate/severe valve)
- Hemodynamically unstable or in cardiogenic shock
- Enrolled in another therapeutic or interventional study
- Off-pump CABG procedure planned
- Limited life expectancy < 1 year
- History of lower extremities venous stripping or ligation
- Inability to provide informed consent

C. Recruitment and Screening

We propose a prospective, multicenter, two-arm, randomized clinical trial (RCT). A block randomization technique will ensure equal distribution of subjects, within each harvester, within each site, in both arms of the trial. The randomization schema will be generated using SAS (SAS, Cary, NC).

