All participating vein harvesters must meet the minimum EVH/OVH volume criteria [at least 100 EVH cases with low conversion rates (<5%) as part of an EVH program established for more than two years] to be eligible to enroll subjects in this study. Unless an urgent medical condition exists, the subject's surgery will be scheduled to occur at the earliest possible date based on expert harvester availability and other center circumstances. The randomization procedure will occur after the participating expert harvester is assigned to the subject. Subjects will be randomized within the assigned participating harvesters to one of the two study harvesting technique arms (EVH or OVH).

Recognizing that the subject's assignment to a participating vein harvester will have already occurred, the study randomization to either EVH or OVH will be done by a telephone call to the Perry Point Cooperative Studies Program Coordinating Center (CSPCC). A block randomization scheme will be used to randomize subjects in two treatment groups. A random sequence of block sizes will be used to reduce the chances of guessing future allocations.

C. Subject Assessments

Baseline assessments will be collected prior to surgery and randomization including Body Mass Index, Ankle-Brachial Index and Venous Clinical Severity Scale. Intraoperative assessments will be collected during the CABG procedure, 24 and 48 hours postoperatively as well as assessments at the time of hospital discharge or 30 days post-surgery, whichever occurs first. Subjects will return for a six-week clinic visit to assess the condition of their leg incision and healing status. Any necessary medical care required will be administered per the Institution's standard practice.

Subjects will receive a phone call every three months for follow-up for events until subject termination. Subjects will complete QoL surveys again at one year either by telephone or mail. If the subject reports a major adverse cardiac event (e.g. MI, repeat revascularization) after discharge from the hospital, then records will be obtained for final adjudication. Ascertainment for death will include review of VA central databases.

Following is a list of assessments/study details that we plan on collecting:

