All participating centers must be able and willing to adhere to the study protocol. The minimum requirements for participating medical centers include:

- Site Principal Investigator: Each center must identify their site's principal surgeon investigator who enthusiastically supports the study and is willing to devote sufficient time and energy to ensure that the study's goals are met. For VA medical centers, the site surgeon investigator must have at least a 5/8th VA appointment for receiving VA research funds.
- EVH/OVH Harvester: Each center/study surgeon investigator must identify their site's harvester(s). The harvester(s) must have performed a minimum of 100 EVH procedures with a conversion rate to OVH < 5% to qualify for participation in the REGROUP trial. Each harvester must also demonstrate competency in OVH or the study surgeon investigator directly attending the case must perform the OVH in the same manner as provided during the course of usual care

absent a clinical trial. A subcommittee of the Executive Committee will convene and review each site's harvester qualifications and issue guidance/recommendations for sites as needed.

- Enrollment Volume: Each center must provide documentation that it will be able to recruit 24 subjects receiving a CABG-only procedure per year into the study who meet all inclusion/exclusion criteria. This total will be 72 subjects receiving CABG-only procedures over the three-year recruitment period.
- Administrative Support: Each center must provide assurance by the Chief of Surgery Service and/or the Chief of Staff that their site investigator will receive full administrative support.
- Multiple Participating Surgeons: At each center, there should be at least one (and preferably two or more) cardiothoracic surgery attending faculty team members participating that agree to randomize and operate on all consenting, eligible subjects with a planned CABG-only on-pump procedure using a median sternotomy incision. Although participating surgeons may enter/leave the study (after approval by the Chairman's office and Perry Point CSP Coordinating Center), the center must make every effort to recruit and to retain at least one qualified participating surgeon to enroll subjects in this study.

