60. Conduit source:	

 	

 If 4 or 9, _____		

 	

 If 4 or 9, _____		

 	

 If 4 or 9, _____				
61. Harvest method:	

 	

		

 	

		

 	

				
62. Conduit quality:	

 	

 If 3 or 8, _____		

 	

 If 3 or 8, _____		

 	

 If 3 or , _____				
63. Conduit size: (mm)	

 	 	

			

 	 	

			

 	 	

		
64. Proximal site:	

 	

		

 	

		

 	

				
65. CASS site:	

 	 	

			

 	 	

			

 	 	

		
66. Distal target size:	

 	

		

 	

		

 	

				
67. Distal disease:	

 	

		

 	

		

 	

				
68. Distal anastomosis:	 Attending Surgeon  Resident/Fellow	 Attending Surgeon  Resident/Fellow	 Attending Surgeon  Resident/Fellow						

S.I. Signature _____

Date _____

VEIN HARVEST CODES		
52. Primary Vein Harvester*	53. Method of Vein Harvest:	54. Conversion from EVH to OVH r/t:
1= PA-C 2= CRNP/CRNFA 3= Attending Surgeon 4= Resident/Fellow 5= other	EVH= Endoscopic OVH= Open	0= NOT APPLICABLE (if 0 then #31=NO) 1= Bleeding (if 1-9 then #31 =YES) 2= Injury to SVG 3= Unacceptable EVH procedure time 4= Insufficient amount of usable vein from EVH procedure 5= Unanticipated graft needed requiring additional vein taken open 6= Harvester unable to locate vein 7= Equipment issue (i.e. contamination, failure, availability) 8= Patient becomes unstable 9= other
55. Harvest Site Closure By:	56. Skin Closure Technique:	

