3. Years of general experience after completion of formal training in chosen profession

<5 years

>5 years but <10 years

>10 years

4. Name of Supervising Physician....._____

5. I have done the following number of **Endoscopic** Vein Harvests (EVH) as of today's date

>100 but <500

>500 but <1,000

>1,000 but <2,000

>2,000

If <100 EVH: STOP!

You are not eligible to participate in CSP #588 at this time.

Please return this Form to [name] at the CSP 588 National Office

6. I have expertise with the following EVH systems

VasoView® (MAQUET)

VirtuoSaph® (TERUMO)

both

SITE NO.

--	--	--

HARVESTER ID

--	--

7. Number of Open (without endoscope; including bridging technique) Vein Harvests (OVH) as of today's date

- <50
- >50 but <100
- >100 but <500
- >500 but <1000
- >1000 but < 2000
- >2000

8. My conversion Rate from EVH to OVH in Last 100 EVH Cases

- 5%
- >3% but <5%
- >1% but <3%
- <1%

9. The above Harvester is experienced in:

both EVH and OVH **EVH only**

Signature of Site Surgeon Investigator

Printed Name of Site Surgeon Investigator

Date

EVENT NO.	SITE NO.	SUBJECT ID	ALPHA CODE	DATE OF NONCOMPLIANCE																						

 	 	

			

 	 	 	

				

 	 	 	 	

					

 	 	 	

				

 	 	

			

 	 	

			

 	 	 	 	

				
				Month	Day	Year																				

FORM 18 – PROTOCOL NONCOMPLIANCE

1. Noncompliance Code

--	--
2. Details (cause of, result, resolution, etc.)

3. Perry Point CSPCC notified on

--	--

--	--

--	--	--	--

Month *Day* *Year*
4. IRB notified on

--	--

--	--

--	--	--	--

Month *Day* *Year*
(code "A" if not notified, note reason in chart)
5. Chairman's Office notified on

--	--

--	--

--	--	--	--

Month *Day* *Year*
9. Did the noncompliance result in a serious adverse event No Yes
(If yes, complete Form 15 – Serious Adverse Event Form)

S.I. Signature _____ Date _____

Protocol Noncompliance Codes

- 01 SAE not reported
- 02 SAE reported late
- 03 Subject not monitored for SAE
- 04 Did not follow instructions from IRB or other review bodies/committees
- 05 Confidentiality or privacy breach

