VA COOPERATIVE STUDY #588

RANDOMIZED ENDO-VEIN GRAFT PROSPECTIVE – REGROUP TRIAL

Site Selection Process: Vein Harvester Qualification Policy

1. VA sites with active Cardiac Surgery Programs are contacted with introductory letter including executive summary and relevant manuscripts via email.
2. Interested sites provide high-level overview of the sites Cardiac Surgery Service eligibility criteria:
 - established EVH program >2years,
 - sufficient isolated CABG volume to enroll 2-3 subjects/month x3 years,
 - willingness to randomize to EVH vs. OVH,
 - at least one harvester experience includes > 100 EVH with conversion rate \leq 5%,
 - ability to competently provide care for OVH procedure.
3. All potential sites complete CSP #588 Form 15 for each individual harvester who is expected to perform the vein harvesting procedure as part of normal daily job duties during the course of study participation at the site. The forms are signed by the site Principle Investigator (site surgeon investigator) as verification.
4. Each completed form is submitted to and reviewed by the Study Chair's office.
5. A Subcommittee of the Executive Committee will review each site case by case to determine eligibility status and designate each site as one of the following:
 - A. Site with at least one harvester experienced in BOTH EVH and OVH confirmed by the site surgeon investigator => site confirmed as qualified for study participation and harvester assigned a code by CSPCC.
 - B. Site with at least one harvester experienced in EVH but NOT OVH confirmed by the site surgeon investigator => site confirmed as qualified for study participation only IF a designated harvester for OVH is identified, assigned a code by CSPCC, and MUST be immediately available, in addition to the EVH harvester, at time of randomization and harvesting (i.e. the site surgeon investigator).
 - I. Site with NO harvester experienced in EVH and/or incapable of providing OVH procedure=> site is INELIGIBLE for study participation at this time regardless of interest level or CABG volume.

Subcommittee Members: [name] [name], FETCS; [name], PA-C; [name], CRNP

CSP #588

RANDOMIZED ENDO-VEIN GRAFT PROSPECTIVE – REGROUP TRIAL

Version 1.2 Protocol

October 1, 2013

F-1

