6.6.3 MACE by OVH Experience

The rate of MACE and its components (all-cause mortality, nonfatal myocardial infarction, & repeat revascularization) will be reported by harvesters' OVH Experience: < 50, > 50 but < 100, > 100 but < 500, > 500 but < 1,000, >1,000 but < 2,000, and >2,000 endoscopic vein harvests completed. A separate table (similar to TABLE 21) will be provided for each level of experience.

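### The forms do not identify who performed the vein harvest, so the harvester-experience analyses can attach the wrong person's experience, mainly to OVH patients

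*Protocol*

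**What the plan says.** **Who may harvest.** Protocol IX.B states "All participating vein harvesters must meet the minimum EVH/OVH volume criteria [at least 100 EVH cases with low conversion rates (<5", followed by the per cent sign and a requirement on the age of the EVH programme. SAP 3.4 repeats it. The bracket has no OVH count. The inclusion criteria (VI.A) ask for "Experienced EVH/OVH harvester and participating surgeon available for procedure". Section XIV adds: "Each harvester must also demonstrate competency in OVH or the study surgeon investigator directly attending the case must perform the OVH". Appendix F category A is a "Site with at least one harvester experienced in BOTH EVH and OVH confirmed by the site surgeon investigator". Category B accepts a harvester experienced in EVH only, provided a designated open harvester with a CSPCC code is on hand at randomisation and harvest; the site surgeon investigator is the example given.

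**Who did harvest.** Form 01 item 18c has one field, for the assigned harvester's ID. Form 05 item 52 is completed for each vein segment using the key "1= PA-C 2= CRNP/CRNFA 3= Attending Surgeon 4= Resident/Fellow 5= other". A footnote defines the primary harvester as whoever spent the most time on the harvest. The form is signed by the site investigator and has no field for a harvester code.

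**How experience is used.** Form 17 holds each harvester's ID, years in practice, EVH volume and, in item 7, "Number of Open (without endoscope; including bridging technique) Vein Harvests (OVH"), in bands from below 50 to above 2,000. SAP 6.6.1 to 6.6.3 tabulate MACE by these bands, the last by "harvesters' OVH Experience: < 50, > 50 but < 100" and upwards. Harvester experience is a named example covariate for the Cox model (Protocol XVII.D.2, Appendix D; SAP 7.1) and for the leg-wound logistic model in Appendix D. Objective 6 asks about its role in clinical outcomes.

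**The concern.** Form 17 experience reaches a patient only through a harvester ID, and the only ID collected belongs to the person assigned before the arm was known. Where someone else took the vein, the patient is analysed under the assigned person's years and volumes.

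This is not confined to deviations. Under Section XIV and category B, the plan itself expects a different operator for open harvests at some sites. The error would therefore fall unevenly between the arms, and it would fall on the variable Objective 6 is meant to study. For example, an EVH-only harvester could well sit in the lowest OVH band. If the surgeon then does that site's open harvests, SAP 6.6.3 would count those patients as harvested by someone with almost no open experience.

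**Working it through.** The plan gives no figure on this point, so the check is to trace what the forms would show in each permitted or foreseeable case. For category B, I assume the site enters the EVH harvester in item 18c; the documents do not say which of the two coded people goes there.

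| Who did most of the harvest | Form 01 item 18c | Form 05 item 52 | Mismatch visible? | Form 17 band used |
|---|---|---|---|---|
| Assigned harvester | own ID | own role | none exists | correct |
| Another person with the same role | assigned ID | same role | no | wrong person's |
| Category B, OVH arm, surgeon harvests | EVH harvester's ID | attending surgeon | yes, by role | wrong person's |
| Category B, OVH arm, designated harvester has the same role | EVH harvester's ID | same role | no | wrong person's |
| Resident does most of a PA's case | PA's ID | resident/fellow | yes, by role | wrong person's |

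Three things follow.

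1. At a category B site, one field completed before allocation cannot be right for both arms. If the site entered the open harvester instead, the error would move to EVH patients. The result does not depend on the assumption; only the arm affected does.
2. Seeing a role mismatch shows that the band is wrong but does not supply the right one. Form 01 item 18d (assigned surgeon ID) helps when item 52 says attending surgeon, but only if that surgeon did the harvest and also has a Form 17.
3. The assigned harvester is fixed before allocation and randomisation is stratified by harvester. An experience band taken from that ID is therefore roughly balanced between arms. The damage is to the experience tables and coefficient. The unadjusted comparison by randomised arm does not use the field.

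**The eligibility wording, side by side.**

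- *OVH:* named in IX.B and SAP 3.4 with no number; competency (or the surgeon performs it) in XIV; confirmed experience or a designated harvester in Appendix F.
- *EVH minimum:* at least 100 in IX.B and SAP 3.4, against "at least one harvester experience includes > 100 EVH with conversion rate" in Appendix F. These differ only at exactly 100 cases.
- *Conversion:* below 5% in IX.B, XIV and SAP 3.4; up to and including 5% in Appendix F. Form 17 item 8 counts the last 100 EVH cases, so the limits are at most 4 and at most 5 conversions. For a true rate of 5%, P(X ≤ 4) = 0.436 and P(X ≤ 5) = 0.616 with X ~ Binomial(100, 0.05). The gap, 0.616 − 0.436 = 0.180, is the chance of exactly 5 conversions and is largest at this rate.

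**The case against.** The strongest reply is that operators are screened and substitutions leave traces. Section XIV and Appendix F require OVH competence or a designated open harvester, the site surgeon signs, the Chair's office sees each form, and a subcommittee rules on each site. Item 52 is recorded per segment, asks for the person who did most of the work, and has a write-in for other roles. Form 18 code 14 covers inappropriate personnel. Section VII.A calls open harvest highly reproducible and Section I says EVH takes longer to learn, so OVH experience may matter little. The SAP 6.6 tables are descriptive and Objective 6 is exploratory.

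All of this stands and limits the size of the point. None of it supplies the missing identity: a same-role switch stays hidden, and code 14 depends on the site reporting it.

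A reader might also infer more than the documents support:

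- *That OVH is unscreened.* It is screened, but by judgement rather than by a count.
- *That the plan admits inexperienced open operators who cannot be detected.* The lowest OVH box on Form 17 carries no stop, but the form also covers people to be marked as EVH only, for whom category B supplies another open harvester. SAP 6.6.3 merely copies the form's bands. Changes of role can be seen.
- *That each low-volume operator accounts for a calculable slice of the OVH arm.* The harvester codes in SAP Table 11 are for patients randomised to EVH, equal caseloads are nowhere stated, and the number of low-volume open operators is not given and could be zero.
- *That MACE or wound results are biased against OVH.* No passage links open-harvest volume to MACE, and neither the share of such harvests nor any excess risk is given.

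**Conclusion.** The point holds as a gap in data collection. The assigned harvester's identity is recorded and the actual harvester's is not, although the plan allows them to differ by arm. SAP 6.6, Objective 6 and any harvester-experience covariate can therefore rest on the wrong person's experience, mainly in OVH patients if category B sites enter the EVH harvester. The number of patients affected depends on how many sites are category B, how often the surgeon does the open harvest, and how often same-role colleagues substitute. The documents give none of these, so I put no figure on it. It does not threaten the unadjusted intention-to-treat result.

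The eligibility wording is a separate, smaller matter of consistency. Whether OVH needs a numeric minimum is open to debate, given the protocol's own view of the technique.

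**What to change.** 1. **Form 05 item 52:** keep the role code and add the CSPCC harvester code of the actual primary harvester for each vein segment. Include an uncoded option that triggers Form 18 code 14.
2. **SAP 6.6 and any harvester-experience covariate:** take experience from that code. Keep the Form 01 ID as the randomisation stratum. State a rule for patients whose segments had different harvesters.
3. **SAP 7.1:** it describes the Cox covariates as baseline characteristics, but the actual operator is settled after allocation and can depend on the arm. Label a model adjusted for that person's experience as explanatory, and show a fit using the assigned harvester's experience beside it.
4. **Eligibility text:** reconcile IX.B, XIV, Appendix F and SAP 3.4 so that one conversion limit and one EVH minimum apply. Either state an OVH criterion or remove OVH from the label, with any threshold left to the investigators. At the same time, correct the form number cited in Appendix F (Form 15; the harvester form is Form 17) and the description of the OVH counts in SAP 6.6.3 as endoscopic.

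The cost is one extra field per segment, plus a code and a Form 17 for everyone who performs open harvests, including surgeons. For patients already operated on, the code would have to come from operative records, if those name the harvester.
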